7.3 Study Completion

Visit Month 12 is the final study visit. Subjects who discontinue the study for any reason at any time should complete all activities associated with the Month 12 visit.

All subjects that complete the Month 12 visit in this study will be offered participation in the long term safety study, Protocol 13VR3. Subjects enrolled in the somavaratan treatment cohort in this study may continue dosing with somavaratan and subjects enrolled in the daily rhGH treatment cohort may transition to dosing with somavaratan in Protocol 13VR3.

8 QUALITY CONTROL AND ASSURANCE

This study will be conducted in accordance with the GCP/ICH consolidated guideline (April 2011). These guidelines include:

- 21 CFR parts 11, 50, 54, 56, 312 and 314
- ICH E2a & ICH E6 (R1)

8.1 Adherence to the Protocol

The principal investigator and all personnel involved with the conduct of the study agree to adopt all reasonable measures to record data in accordance with the protocol. Under practical working conditions, however, some minor variations may occur due to circumstances beyond the control of the investigator(s). All such deviations will be documented in the study records, together with the reason for their occurrence; where appropriate, deviations will be detailed in the clinical study report and provided in a timely manner to the Sponsor, Sponsor's designee and research site IRB per IRB guidelines.

Quality assurance audits of the clinic and study practices/procedures may occur. Any findings from quality assurance audits related to the study will be reported to the Sponsor.

9 PLANNED STATISTICAL METHODS

9.1 General Considerations

Summaries of subject disposition, demographics, disease characteristics and response to dosing of study medication will be provided for each treatment group. All summaries of continuous data will be presented as means (SD), and/or with medians with min/max as appropriate. Count data will be presented as number within each treatment group and % of subjects within each group.

Summaries of all adverse events (AEs), serious adverse events (SAEs) and Suspected, Unexpected Serious Adverse Reactions (SUSARs) will be reported. The incidence of CTCAE Grade 3 or 4 adverse events will be classified according to severity and relationship to study drug. Standard statistical methods will be employed to analyze all data. It is anticipated that the following techniques may be used: descriptive statistics, t-test, paired t-test, McNemar's/Bowker's test, ANOVA, ANCOVA, and graphical displays. Assumptions of normality and homogeneity of variance will be tested with the Shapiro-Wilks test. If the normality distributional assumptions are violated, non-parametric techniques, such as Wilcoxon's Rank-Sum test and the Kruskal-Wallis test, will be employed as appropriate.

The study is open-label. The Sponsor and Investigators will be blinded to-aggregate height velocity data throughout the trial.

Study sites will be pooled into two Regions: North America and Europe. The randomization will be stratified by Region, age (above and below anticipated median age of 7.5 years) and for baseline IGF-I SDS (above and below anticipated median of -1.7). Randomization tables will be prepared by the CRO. Randomization assignments will be made upon approval of subject eligibility by the medical monitor.

An intention to treat (ITT) population will be used for the primary evaluation of efficacy. The primary endpoint will be the non-inferiority of somavaratan treatment height velocity compared to daily rhGH after 12 months on treatment. For subjects completing less than the 12 months of treatment, missing height at 12 months will be imputed from the last available height SDS, with a reduction of 2 cm/yr for subjects in the somavaratan group. This imputation calculates the height at 12 months from the height SDS observed at study exit. This is equivalent to a subject not having gained any more height relative to the age specific height (i.e., no treatment response) since study exit. The reduction of 2 cm/yr, the non-inferiority margin, only for the somavaratan imputed value avoids imputing to a common mean.³¹ A sensitivity analysis using multiple imputation technique, assuming missing at random, will also be conducted. Baseline characteristics of these dropped subjects will be reported. A per protocol analysis for subjects completing 12 months of treatment with <10% missed or

incorrect dosing will also be performed. No imputations will be considered for the PP populations.

For the growth and bone age endpoints, the least squares means and confidence interval of the treatment groups from an ANCOVA model will be used to determine non-inferiority. The ANCOVA model will use the endpoint (e.g., height velocity) as the dependent variable, with treatment and region as fixed effects, and include age, baseline IGF-I SDS as covariates. Other covariates will be considered as appropriate. The potential treatment differences in IGF-I and IGFBP-3 responses will be evaluated with ANCOVA, with treatment and region as fixed effects, and baseline characteristics as covariates as appropriate.

The gender, age, height and weight of subjects entering puberty at one year will be described. Onset of puberty is defined as the appearance of Tanner stage 2 breast development in girls and a testicular volume ≥ 4 mL in boys.

An exploratory analysis will be conducted to determine if IGF-I responses correlate to height velocity outcomes.

Mean values and mean change from baseline for safety laboratory data will be summarized by visit and treatment group. If applicable, appropriate statistical methods may be employed to look for trends in safety variables. No formal tests of hypotheses are planned for safety parameters and no corrections for multiple comparisons will be made.

A detailed Statistical Analysis Plan will be developed before the first subject begins study drug.

Version 9.4 or higher of the SAS® statistical software package will be used to provide all statistical analyses.

9.2 Determination of Sample Size

Between 84 and 136 subjects are expected to complete the study. Sample size estimates are derived from considerations for non-inferiority testing of twice-monthly somavaratan versus daily rhGH. The somavaratan treatment cohort will be tested against the daily rhGH treatment cohort using a one-sided test procedure. Assuming a 3:1 somavaratan to daily rhGH subject ratio for each comparison, a standard deviation of ≤ 3.0 cm/yr. in annual height velocity, an alpha of 0.05 and a non-inferiority limit for difference in mean height velocity of 2.0 cm/yr., a total of 76 subjects are required: 57 for the somavaratan treatment cohort and 19 for the daily rhGH treatment cohort. The total number of planned subjects is 84 (76 plus 8 for potential drop-outs).

A non-inferiority margin of -2.0 cm/yr is chosen for analysis of the primary endpoint. This margin was used for the approval of Valtropin®. The margin is considered conservative when compared to the distribution of first year height velocities for children with similar degrees of GHD and treated with daily rhGH in a dose similar to the daily rhGH treatment cohort of this study. For children with moderate (“less severe”) GHD, ages 4 to 10, the differences between the 3rd and 50th percentile for the first year height velocity is approximately 3–4.5 cm/yr.

An independent statistical consulting group will conduct sample size re-estimation using the observed variance in height velocity to determine if *a priori* assumptions were valid and notify the Sponsor if the total sample size should be increased to ensure statistical analyses with adequate power. If the assumption of variance in height velocity has been underestimated as determined in the sample size re-estimation procedure, the sample size may be increased up to 136 subjects.

9.3 Analysis Populations

9.3.1 *Safety Population*

The safety population will consist of all subjects completing a screening evaluation and receiving any amount of study drug.

9.3.2 *PK/PD Population*

The PK/PD analysis population will consist of all subjects receiving study drug and having at least one post-treatment PK/PD assessment. A PK/PD per protocol subset will include all subjects with complete PK/PD assessments and no missed doses in the dosing interval prior to a PK/PD assessment.

9.3.3 *Intent-to-Treat Population*

The intention to treat analysis (ITT) will be the primary analysis population. The ITT population will consist of all subjects completing at least one month of dosing with completed efficacy assessments at the Month 1 Visit. For subjects completing less than the 12 months of treatment, the height velocity at 12 months will be imputed from the change from baseline of last measurement of HT-SDS. With this procedure, a 12 month height velocity measurement will be available for all subjects in the ITT.

Baseline characteristics of the excluded subjects will be reported. In the event that numerous imputations are required, comparisons of subject that completed versus those who dropped and required imputation will be done.

9.3.4 *Per Protocol Population*

A per protocol analysis will be used to evaluate efficacy parameters. All subjects completing one year of continuous study dosing with efficacy assessments at Month 12 will be included. Patients with major dosing deviations ($\geq 10\%$ of total assigned doses missed) will be excluded from per protocol analysis. Missing data for the per protocol population will not be imputed.

9.4 Demographics and Baseline Characteristics

Demographic and baseline characteristics to be collected include:

Gender

Race/Ethnicity

Measured maternal and paternal heights (where available)

Birth history (weight, length, gestational age at birth)

Prior height velocity assessed from 6 or more months observation (where available)

Bone age results and date of examination

GH stimulation tests (date, agents used, maximal GH response)

Adrenal test results (morning cortisol or stimulation test). If stimulation test, specify date test agent used and maximal cortisol response

9.5 Primary Endpoints

The primary efficacy endpoint is:

- Annual height velocity after 12 months continuous treatment with either somavaratan or daily rhGH

9.6 Secondary Endpoints

The secondary efficacy endpoints are:

- Change in height SDS
- Change in bone age relative to chronological age (BA/CA)
- Change in Body Mass Index
- Change in body weight

- IGF-I and IGFBP-3 responses to study drug administration and their relationship to height velocity will be evaluated.

9.7 Retention of Data

All primary data generated in the study and described by RPG (or copies thereof [e.g., laboratory records, data sheets, correspondence, photographs and computer records]), which are a result of the original observations and activities of the clinical study, and are necessary for the reconstruction and evaluation of the study report, will be retained in the RPG archive for a period of 5 years after issue of the final report. At this time, the Sponsor will be contacted to determine whether the data should be returned, retained or destroyed on their behalf. No data will be destroyed without the agreement of the Sponsor.

All study-related records must be retained until 2 years after the last approval of a marketing application in an ICH region and until there are no pending or contemplated marketing applications in an ICH region or at least 2 years have elapsed since the formal discontinuation of clinical development of the investigational product. The Sponsor will inform the PI/Institution when the documents no longer need to be retained. The PI must obtain approval in writing from the Sponsor prior to destruction of any records. Typically, these records will be held in the PI's archives. If the PI is unable to meet this obligation, the PI must obtain permission from the Sponsor to make alternative arrangements. Details of these arrangements must be documented in writing to the Sponsor.

Specimens requiring frozen storage are specifically excluded from the above. These will be retained for as long as the quality of the material permits evaluation but for no longer than 6 months after completion of the study (defined as issuance of Clinical Study Report). The Sponsor will be notified of the intent to destroy samples and any financial implications before specimens are destroyed on their behalf.

9.8 Interim Analysis

No interim analysis is planned.

9.9 Other Analyses

Estimation of PK and PD parameters (e.g., C_{max} , average concentration) will be performed using non-compartmental methods. Post hoc PK/PD models of IGF-I response to somavaratan and rhGH may be evaluated using appropriate methods.

Pubertal development will be described. Findings from 12-lead ECGs will be described.

In addition, the relationship of the presence of ADAs will be explored. The subjects will be classified as ADA negative, transient or persistent based on Shankar et al., and the relationship of this ADA classification with PK, PD and clinical endpoints will be evaluated.³⁰

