4.4 Subject Withdrawals and Replacements

Consent may be withdrawn at any time for any reason by subject or subject caregiver without prejudice to future treatment. The investigators or medical monitor may withdraw a subject if it is judged to be in the best interest of the subject or if it is clear the subject cannot comply with the protocol. For early withdrawals, the tests and evaluations listed for the Month 12 visit should be completed, if possible.

Subjects that develop a new significant medical condition at any point during the trial may be withdrawn.

To achieve the planned sample size for analysis, additional subjects will be enrolled as needed to account for subjects who withdraw prior to completing one month of treatment and Month 1 height evaluations.

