The safety, pharmacokinetic and pharmacodynamics assessments require blood samples to be collected during the study. The total blood volume required to be collected over the course of the study including the screening visit has been minimized and is provided in Table 4.

Table 4 Maximum Blood Volumes Required

Sample Type	Blood Volume (mL) per Sample	Collection Schedule							Total Number of Occasions	Total Per Subject (mL)
		Screening	Day 1	M1	M3	M6	M9	M12		
Hematology	2.0	X		X		X		X	4	8.0
Chemistry	4.0	X		X		X		X	4	16.0
PD ¹	4.0	X	X	X	X	X	X	X	7	28.0
PK ²	2.0		X	X	X	X	X	X	6	12.0
Antibodies	3.0	X		X	X	X	X	X	6	18.0
HbA1c	2.0	X		X		X		X	4	8.0
Total Blood Volume (mL) Required For Study									90.0	

1: May include IGF-I, IGFBP-3, GHBP and ALS (refer to Appendix 1)

2: PK collected in the somavaratan treatment cohort only

To ensure subject safety, no more than 17 mL (and not to exceed 2 mL/kg) of blood will be collected from individual subjects at any specific time point and will not exceed 4 mL/kg in any 30-day blood collection period.

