6.4 HANDLING OF MISSING VALUES AND OUTLIERS

Because of subject privacy limitations, birth dates may only be reported by month and year in certain locations. Where the specific birth day is not available, the day of month will be imputed as the 15th.

For the primary endpoint in the ITT population, missing height at 12 months will be imputed from the last available height. This imputation assumes no growth after the last available measurement observed at study exit. This is an extremely conservative approach. For example, a █ year old █ subject who discontinued at month 6 with annualized HV of 6 cm/yr (Day 1 height of █ cm and Month 6 height of █) will have the height at 12 months imputed to █ cm, resulting in an annual HV of 3 cm/yr.

For the sensitivity analysis of the effect of missing data on the primary endpoint, height velocity at Month 12, a tipping point approach will be used. The missing data will be imputed as follows:

For the control group:

1. All subjects to the control group mean (calculated without subjects missing endpoint)
2. 50% to the group mean, 50% to the HV associated with each subjects last reported height (no additional gain in height)
3. Each subject's HV imputed based on its own last reported height

For the somavaratan group:

1. All subjects to the somavaratan group mean (calculated without subjects missing endpoint)
2. 50% to the group mean, 50% to the HV associated with each subjects last reported height (no additional gain in height)
3. Each subject's HV based on its own last reported height
4. Each subject imputed to HV based on last reported height, minus 1 cm.
5. Each subject imputed to HV based on last reported height, minus 2 cm (the non-inferiority margin, to avoid imputing to a common mean).

The reduction of the imputed HV by -1 and -2 cm will be limited to a minimum 0 HV, as negative HV is not possible. This will result in a total of 15 comparisons which should cover the range of plausible results for the subjects who are not able to provide Month 12 height velocity, and accounts for combinations where the somavaratan drop outs will have worse outcomes than drop outs in the control group (e.g., control group imputation 1 versus somavaratan imputations 2 to 5).

No imputations will be considered for the PP populations.

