6.12.3 Immunogenicity/Antibodies

Immunogenicity of somavaratan and daily rhGH will be assessed by measurement of anti-drug antibodies (ADAs) in serum samples. ADAs to both somavaratan and daily rhGH will be determined following a tiered approach consisting of screen, confirmation, titration and additional characterization. The additional characterization of somavaratan ADAs includes measurement of ADA specificity to rhGH and XTEN and neutralization capacity in an *in*

vitro cell bioassay. A summary of the ADA results will be described in detail in a separate immunogenicity analysis report included in the Integrated Summary of Immunogenicity (ISI).

The effect of ADAs on height velocity (HV) and safety will be evaluated for both treatment groups. An analysis of variance (ANOVA) model of HV as dependent variable with treatment and ADA classification (e.g., positive/negative status (c.f., Shankar et al., 2014); based on titer, etc.) as factors will be used as the first step in this evaluation. Comparisons of somavaratan PK, IGF-I and IGF-SDS between the ADA classification groups will also be performed. The additional characterization data will also be assessed for relevance to HV.

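### ADA class builds up over follow-up and is then related to height velocity over the same year; if early leavers enter with imputed growth, the comparison tends to make ADA look less harmful

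*Protocol*

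**What the plan says.** Protocol 9.9: "The subjects will be classified as ADA negative, transient or persistent based on" a cited publication, and "the relationship of this ADA classification with PK, PD and clinical endpoints will be evaluated". The class rule itself is not written out.

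SAP 6.12.3: "The effect of ADAs on height velocity (HV) and safety will be evaluated for both treatment groups". The first step is "An analysis of variance (ANOVA) model of HV as dependent variable with treatment and ADA classification" as factors. The SAP's examples of the class are positive/negative status or titer. It names no analysis population, no rule for missing HV, no minimum number of samples and no landmark for this model.

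Sampling (Protocol 6.6.2 Table 4, Appendices 1 and 2): antibodies are drawn at Screening and at Months 1, 3, 6, 9 and 12 in both arms. On early exit (Protocol 4.4): "For early withdrawals, the tests and evaluations listed for the Month 12 visit should be completed, if possible". Those tests include immunogenicity.

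Missing 12-month height: SAP 6.4 carries the last height forward for the primary endpoint in the ITT set: "This imputation assumes no growth after the last available measurement observed at study exit". Protocol 9.1 has a different rule, in which the missing height is "imputed from the last available height SDS, with a reduction of 2 cm/yr for subjects in the somavaratan group". Protocol 9.3.3 says that these procedures give every ITT child a 12-month HV. No imputation is done in the per-protocol set.

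**The concern.** Length of follow-up feeds both sides of the comparison. A completer has five post-dose chances to test positive. A child who leaves at Month 3 has two scheduled ones, plus an exit sample if it is obtained separately. Short follow-up therefore lowers the chance of being classed positive or persistent. Under the SAP's ITT rule it also lowers the 12-month HV. The two together create an association between ADA class and growth even when ADA has no effect.

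At stake is how the trial reads the effect on growth of antibodies to a new fusion protein. ADA responses are among the secondary objectives (Protocol 2.2), and ADA results also go into an integrated immunogenicity summary (SAP 6.12.3). A modest true loss of growth could be masked.

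**Working it through.** **Figure in the plan.** Table 4 gives 6 antibody occasions: Screening plus Months 1, 3, 6, 9 and 12. 6 × 3.0 mL = 18.0 mL, as stated. Five are post-dose.

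**Inputs from the documents.** Dropout 8/84 = 9.5% (Protocol 9.2). Mean first-year HV 10 cm/yr, within the 9.5–11 of Protocol Section 1. SD 3.0 cm/yr (Protocol 9.2). Zero growth after exit (SAP 6.4).

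**Assumptions not in the documents.** 40% of children ever ADA-positive, onset equally likely at each of the five visits, 60% of positives lasting. Persistent means at least two positive samples. Exit is equally likely at Months 1, 3, 6 and 9, with a sample at exit, and is unrelated to ADA. ADA has no true effect on HV.

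**Class probabilities.**
- Positive: completers 0.40; leavers 0.40 × mean(1, 2, 3, 4)/5 = 0.20.
- Persistent: completers 0.40 × 0.60 × 4/5 = 0.192; leavers 0.40 × 0.60 × mean(0, 1, 2, 3)/5 = 0.072.

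**Who is in each class, per 84 children (76 completers, 8 leavers).**
- Negative: 76 × 0.60 = 45.6 completers and 8 × 0.80 = 6.4 leavers, so 12% leavers.
- Persistent: 76 × 0.192 = 14.59 completers and 8 × 0.072 = 0.58 leavers, so 4% leavers.

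**Mean HV.** A leaver at month m has imputed HV 10 × m/12.
- Negative leavers, weighted by the chance of still being negative at exit (0.92, 0.84, 0.76, 0.68): 10 × (0.92×1 + 0.84×3 + 0.76×6 + 0.68×9)/(3.2 × 12) = 3.68.
- Persistent leavers, weights 0, 1, 2, 3: 10 × (0×1 + 1×3 + 2×6 + 3×9)/(6 × 12) = 5.83.
- Negative class: (45.6 × 10 + 6.4 × 3.68)/52.0 = 9.22.
- Persistent class: (14.59 × 10 + 0.58 × 5.83)/15.17 = 9.84.
- Difference with no true effect: 9.84 − 9.22 = **+0.62 cm/yr**.

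A simulation of the same case gave +0.63. It was then varied:

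| Setting (no true ADA effect, persistent minus negative unless stated) | Bias, cm/yr |
|---|---|
| 9.5% dropout, ADA rate 20–70% and onset uniform or early | +0.39 to +1.06 |
| 5% dropout, same range | +0.24 to +0.60 |
| 20% dropout, same range | +0.80 to +1.99 |
| Persistent = positive at last sample | +0.48 |
| Positive minus negative | +0.55 (+0.24 to +0.98) |
| Protocol imputation (assumes 5.5 cm/yr background growth) | about +0.43 |
| Completers only | 0.0 |
| Lasting ADA raises exit 3- to 8-fold | +0.36 to −0.72 |

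**Masking, base case.** A true −0.5 cm/yr reads +0.10, −1.0 reads −0.35, and −2.0 reads −1.35 (−0.87 if 70% are ever positive).

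**Precision.** With 63 somavaratan children, 60% negative and 20% persistent, SE = 3 × √(1/37.8 + 1/12.6) = 0.98 cm/yr. Across 63–102 children and the class shares tried, it is about 0.7–1.0.

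**Landmark.** Class was fixed from the Month 1, 3 and 6 samples in children still on study at Month 6: (76 + 4)/84 = 95%. Each then has the same number of samples. The null bias was 0.00 (uniform onset) and −0.01 (early onset), against +0.63 and +0.45 as planned. A true −2.0 read −1.7 to −1.9, against −1.4 to −1.5. This check kept 12-month HV as the outcome. The equal-sampling argument carries over to Month 6–12 growth.

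**The case against.** The strongest reply is that the plan does not say the zero-growth fill applies here. SAP 6.4 writes it for the primary endpoint in the ITT set, and the ADA model names no population. In completers the null bias is zero. If a leaver's HV were simply annualised to the last height, as the general formula in SAP 6.11.1 would allow, the simulated bias is also zero. This stands, and the point is therefore conditional. But SAP 6.11 leads with all randomised children, and Protocol 9.3.3 supplies an imputed HV for each ITT child, so the biased version is a natural default and nothing rules it out.

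A reader might infer that persistent ADA must look harmless by construction, or that every antibody-driven exit counts against the non-persistent group. The documents support neither. A child who leaves because of ADA may already be positive, and an exit sample is requested. Withdrawal for poor growth looks back six months (Protocol 3.5.2.1), so it would normally follow several samples. With ADA-driven exit the sign can turn.

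It is also fair that the analysis is exploratory, that the ANOVA is called a first step, that a separate immunogenicity report is planned, and that the central bias lies within one standard error. These limit the weight of the point. They are no reason to keep an avoidable bias.

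**Conclusion.** The point holds in conditional form. Follow-up time drives both ADA class and, if imputed HV is used, the outcome. With exit unrelated to ADA and 9.5% dropout, the bias favours positive or persistent ADA by about 0.4 to 1.1 cm/yr. That can hide a true loss of about 0.5 cm/yr and attenuates a 2 cm/yr loss without erasing it. The size rests on assumed ADA rates, onset and class definition, none of which the documents give. The direction rests on why children leave. The mechanism applies to the Protocol's three-way class and to the SAP's positive/negative example alike. The primary non-inferiority test is not affected. This is a cheap improvement to a secondary, exploratory analysis, not a defect in the main result.

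**What to change.** In SAP 6.12.3:

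1. Add a landmark analysis: ADA status from samples through Month 6 against growth from Month 6 to Month 12, in children still on study at Month 6. Say how children who leave after Month 6 are handled.
2. State that the ANOVA of 12-month HV on ADA class uses observed, not imputed, Month 12 height, and write out the class rule.
3. List the early leavers with their ADA results. Restriction to observed height could otherwise remove children lost through ADA-related failure, so it should accompany the landmark and not replace it.
4. Report ADA incidence by visit, with the number sampled as denominator.

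The cost is SAP wording, one or two tables and a listing. Heights and antibodies are already collected at Months 6 and 12, and Protocol 10.10 allows SAP changes before database lock. The downsides are that a few early leavers (about 8 of 84 at planned dropout) leave the ANOVA, and that the landmark uses only second-half growth and counts ADA first seen after Month 6 as negative.
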